##### 11.1.1.2. Sample Size Parameters for the Primary Endpoint

The sample size parameters for the primary endpoint are shown below.

- Expected Control rate  $P_{\text{Control}}$ : 4%
- Expected Sentinel (test) rate  $P_{\text{Sentinel}}$ : 2% (50% relative reduction)
- Test significance level ( $\alpha$ ): 0.05 (2-sided)
- Power ( $1 - \beta$ ): > 0.90 (see **Note 1** below)
- Test to Control ratio: 1:1 (see **Note 2** below)
- Number of evaluable subjects: up to 6000 maximum enrollment with sample size re-estimation
- Planned enrollment: = 3000 subjects (N=1500 per cohort)

The statistical approach uses an adaptive group sequential design. There will be 1 planned formal interim analysis performed on the first 70% of enrolled subjects (N=2100) by the Independent Safety and Statistical Monitor (see Section 21.3). The study will be stopped if a significant difference in favor of the test arm is observed after this interim analysis.

Based on the results of the interim analysis, sample size re-estimation may be performed and the sample size may be increased up to a maximum of 6000 subjects. Details of this adaptive approach are pre-specified in the Independent Safety and Statistical Monitor charter. A final analysis will be performed on all enrolled subjects if the study is not stopped after the interim analysis (see Section 11.1.1.3 and Section 11.3.2 below).

**Note 1:** This power calculation includes sample size re-estimation.

**Note 2:** Randomization will occur at the index procedure (prior to procedural puncture/incision) to avoid selection/treatment bias.

#### 11.1.1.3. Success Criteria for the Primary Endpoint

As noted above, 1 planned formal interim analysis for the primary endpoint will be conducted on the first 70% of enrolled subjects and a final analysis will be conducted on all enrolled subjects if the study is not stopped after the interim analysis. The alpha-level for the interim analysis and the final analysis is adjusted using the Lan-Demets spending function with O'Brien-Fleming boundaries as detailed below in Section 11.3.2. If the *P* value from the chi square test is less than alpha and the rate in the Sentinel group is less than the rate in the Control group, the group with Sentinel will be concluded to have a lower rate of all stroke through 72 hours post TAVR procedure or hospital discharge (whichever comes first) compared to the Control group.

#### 11.1.1.4. Statistical Methods – Primary Endpoint

All subjects who are enrolled will be eligible for evaluation. Handling of dropouts and missing data will depend on their frequency and the nature of the outcome measure. Methods to eliminate or minimize bias will be implemented and described completely, if applicable. Outlier values will be evaluated for their validity. Suspected invalid data will be queried and corrected in the database prior to statistical analysis.

### 11.1.2. **Post-procedure Measurements**

Post-procedure data will be collected as detailed in the clinical study schedule (**Table 10.1-1**) and will be summarized using descriptive statistics for continuous variables (e.g., mean, standard deviation, n, minimum, maximum) and frequency tables or proportions for discrete variables. Adverse event and SAE rates will be reported.

### 11.2. **General Statistical Methods**

All statistical analyses will be performed using the SAS System software, version 9.2 or later (Copyright© 2000 SAS Institute Inc., [name]. All rights reserved).

All statistical analyses will be conducted according to applicable Standard Operating Procedures, Work Instructions, and the study-specific statistical analysis plan.

### 11.2.1. Analysis Sets

The primary endpoint and the additional measurements will be analyzed on an ITT basis and a Per-Protocol basis. For ITT analyses, all subjects who sign the IRB/IEC/HREC-approved study ICF (see Section 10.3) and are enrolled in the trial (see Section 9.1) will be included in the analysis, whether or not the assigned treatment is received. For Per-Protocol analyses, ITT subjects who undergo TAVR and who are treated as assigned in the randomization process (excludes crossovers) will be included in the analysis.

### 11.2.2. Control of Systematic Error/Bias

The selection of subjects will be made from the Investigator's usual case load. All subjects who have signed the ICF, are deemed treatable with the Sentinel device (have suitable anatomy per the IFU) and are selected to undergo TAVR with a commercial TAVR device will be eligible for enrollment in the study. The study center's heart team assessments and imaging measurements before device placement will contribute to the determination of subject eligibility for the study.

To control for inter-observer variability, an independent CEC (see Section 21.1) will adjudicate pre-determined endpoints.

### 11.2.3. Number of Subjects per Investigative Center

A single center may enroll up to 15% of the total enrollment; approval from the Sponsor is required for additional enrollment.

### 11.2.4. Randomization Scheme

Using a computer-generated list of random treatment allocations (i.e., a randomization schedule) subjects to be treated with a commercially available TAVR device will be randomized 1:1 into a Test cohort using the commercially available Sentinel device or a Control cohort with no cerebral protection system. Randomization will be stratified by center, by operative risk (low risk and intermediate or higher risk; see surgical risk definitions in Table 25.2-1), and by intended TAVR valve type (balloon-expandable device and non-balloon expandable device). Additional information is provided in the study Manual of Operations.

## 11.3. Data Analyses

Baseline and outcome variables will be summarized using descriptive statistics for continuous variables (mean, standard deviation, number of observations, minimum and maximum) and discrete variables (percentage and count/sample). See Section 11.1.1 for a discussion on analysis of the primary endpoint.

### 11.3.1. Other Endpoints/Measurements

Other measurements not driven by statistical hypotheses are listed in Section 6.2.2.

### 11.3.2. Interim Analyses

One formal interim analysis is planned for the purpose of stopping this trial early for effectiveness. This analysis will be performed by the Independent Safety and Statistical Monitor (see Section 21.3). The interim analysis for the primary endpoint will be conducted on the first 70% of enrolled subjects; a final analysis will be conducted on all enrolled subjects if the study is not stopped after the interim analysis.

The Lan-Demets spending function with O'Brien-Fleming boundaries is used to adjust the alpha-level for the interim analysis and the final analysis (if needed): 0.0148 and 0.0455, respectively. If the *P* value from the chi-square test is less than alpha, and the rate in the Sentinel group is less than the rate in the Control group, the group with Sentinel will be concluded to have a lower rate of all stroke through 72 hours post TAVR procedure or discharge (whichever comes first) versus the Control group and the study will be stopped. If the study is not stopped after the interim analysis, sample size re-estimation may be performed contingent on the results of the interim analysis (see Section 11.1.1.2).

The planned interim analysis is pre-specified to provide a formal hypothesis testing approach to examine the primary endpoint with the adjusted significance level and stop the trial early for effectiveness if appropriate. This pre-specified interim analysis allows for sample size re-estimation per the study's adaptive group sequential design.

Additional analyses not defined in the protocol may also be conducted for regulatory agency review.

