	
EC6. Subject is contraindicated for anticoagulant and antiplatelet therapy.
 
Note 4: Use of general anesthesia during TAVR may affect neurocognitive function shortly after the procedure. While not an exclusion criterion, it is recommended that general anesthesia not be used if possible.

Adjunctive Pharmacologic Therapy	Management of subjects in both groups, including antiplatelet and anticoagulant medications, is left to the discretion of the treating physician.
Statistical Methods	
Analysis Sets	
Analysis sets are listed below.
 
Intention-To-Treat (ITT): This population includes all subjects who sign an ICF and are enrolled in the trial (randomized), whether or not the assigned treatment is received.
 
Per-Protocol: This population includes all ITT subjects who undergo TAVR and who are treated as assigned in the randomization process (excludes crossovers).

Statistical Hypothesis for the Primary Endpoint	The rate of the primary endpoint (all stroke through 72 hours post TAVR procedure or hospital discharge [whichever comes first] as adjudicated by an independent CEC) in the Sentinel (Test) cohort is superior to that in the Control cohort.
Statistical Test Method for the Primary Endpoint	
A chi-square test will be used to test the two-sided hypothesis of superiority of Sentinel versus the Control:
 
<math>H_0: P_{\text{Sentinel}} = P_{\text{Control}}</math>
 
<math>H_1: P_{\text{Sentinel}} \neq P_{\text{Control}}</math>
 
where <math>P_{\text{Sentinel}}</math> and <math>P_{\text{Control}}</math> correspond to the rates of the primary endpoint for the Sentinel group (test) and the Control group (no cerebral protection), respectively.
 
The primary analysis set is the ITT analysis set; this endpoint will also be analyzed for the Per-Protocol analysis set.

Sample Size Parameters for the Primary Endpoint	
Sample size parameters are listed below.
 
 
• Expected Control rate <math>P_{\text{Control}}</math>: 4%
 
• Expected Sentinel (test) rate <math>P_{\text{Sentinel}}</math>: 2% (50% relative reduction)
 

PROTECTED TAVR: Stroke PROTEction with SEntinel During Transcatheter Aortic Valve Replacement	

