**Table 6.3-1: Overview of Objectives and Endpoints**

Objective	Endpoint	Rationale for Endpoint
Primary Endpoint		
Evaluate effectiveness of the cerebral protection device during TAVR procedures	All stroke to 72 hours post-TAVR procedure	Demonstrate significant reduction of peri-procedural stroke (≤72 hours) after TAVR, which is a critical acute safety event observed in the population undergoing TAVR.
Additional Measurements of Safety and Effectiveness		
Evaluate safety of the cerebral protection device	Safety measures peri- and post- TAVR procedure and at discharge	Confirm safety based on assessments recommended by VARC  and NeuroARC  for this elderly population.

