### **21.3. *Independent Safety and Statistical Monitor***

The unblinded data from the first 70% of enrolled subjects will be reviewed by the Independent Safety and Statistical Monitor (independent of the project team). The study will be stopped if a significant difference in favor of the test arm is observed after this interim analysis (see Section 11.3.2). Based on the results of the interim analysis, sample size re-estimation may be performed and the sample size may be increased up to a maximum of 6000 subjects. Details of this adaptive approach are pre-specified in the Independent Safety and Statistical Monitor charter.

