## **22. Suspension or Termination**

### **22.1. *Premature Termination of the Study***

Boston Scientific Corporation reserves the right to terminate the study at any stage but intends to exercise this right only for valid scientific or business reasons and reasons related to protection of subjects. Investigators, associated IRBs/IECs/HRECs, and regulatory authorities, as applicable, will be notified in writing in the event of study termination.

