#### **22.1.1. *Criteria for Premature Termination of the Study***

Possible reasons for premature study termination include, but are not limited to, the following:

- The occurrence of unanticipated adverse device effects that present a significant or unreasonable risk to subjects enrolled in the study.
- An enrollment rate far below expectation that prejudices the conclusion of the study.
- A decision on the part of BSC to suspend or discontinue development/marketing of the device.

This trial may also be stopped early for effectiveness if upon interim analysis a significant difference in favor of the test arm is observed after enrollment of the first 70% of subjects. Please see Section 11.3.2 for additional information.

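### Does a two-sided interim test with a stopping rule for benefit only leave an excess of strokes on Sentinel without a response?

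*Combined protocol and SAP*

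**What the plan says.** The Synopsis states the test: "A chi-square test will be used to test the two-sided hypothesis of superiority of Sentinel versus the Control". Overall alpha is 0.05 two-sided, and Section 11.3.2 sets nominal levels of 0.0148 at the interim and 0.0455 at the final analysis. The success rule in Sections 11.1.1.3 and 11.3.2 has two parts: a P value below the level, and a lower stroke rate on Sentinel than on Control.

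Section 11.3.2 gives the purpose of the look: "One formal interim analysis is planned for the purpose of stopping this trial early for effectiveness". The stopping rule runs in one direction. Section 11.1.1.2 puts it this way: "The study will be stopped if a significant difference in favor of the test arm is observed after this interim analysis". The Synopsis and Sections 7.3, 11.3.2, 21.3 and 22.1.1 agree. For every other interim result, Sections 11.1.1.2 and 11.3.2 provide for a final analysis on all enrolled subjects, and Section 11.3.2 adds: "If the study is not stopped after the interim analysis, sample size re-estimation may be performed contingent on the results of the interim analysis".

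The look is taken by a party independent of the project team. Section 21.3: "The unblinded data from the first 70% of enrolled subjects will be reviewed by the Independent Safety and Statistical Monitor". That monitor works to a charter, which the protocol cites for the details of the adaptive approach.

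Stopping for other reasons is covered separately. Under Section 22.1 the sponsor may end the study at any stage, "only for valid scientific or business reasons and reasons related to protection of subjects". Section 22.1.1 opens its list with "Possible reasons for premature study termination include, but are not limited to, the following", and its first item is unanticipated adverse device effects that pose a significant or unreasonable risk.

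**The concern.** The primary endpoint is also a safety outcome. Table 6.3-1 describes peri-procedural stroke as something "which is a critical acute safety event observed in the population undergoing TAVR". The interim is the only formal comparison of the arms before the final analysis.

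Read literally, a significant excess of strokes on Sentinel falls under the heading of a study that was not stopped. Enrollment would go on, and nothing in the text rules out a larger sample size. No section gives a between-arm threshold for harm, or says what the monitor must report and to whom. If that silence decided the outcome, up to 450 more subjects could be assigned to Sentinel in the planned 3000 after the device had looked harmful at a strict level.

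**Working it through.** **Inputs.** Interim at 70% information, N = 2100, so 1050 per arm; planned N = 3000, 1500 per arm; expected stroke rates 4% on Control and 2% on Sentinel; two-sided alpha 0.05; Lan-DeMets spending of O'Brien-Fleming type (Sections 11.1.1.2 and 11.3.2). Enrollment of 3000 in about 30 months (Section 7.1), or about 100 per month. Harmful Sentinel rates and the length of the interim review are not in the documents; they are assumed and shown as ranges.

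**1. Reproduce the plan's levels.** With 0.025 in each tail, the amount spent per tail at t = 0.7 is 2[1 − Φ(z₀.₉₈₇₅/√0.7)] = 2[1 − Φ(2.241/0.8367)] = 0.00738. Doubled, this is 0.01477, which rounds to the stated 0.0148 (critical z = 2.438). Solving the bivariate normal with correlation √0.7 gives 0.0455 at the final analysis (z = 2.000). Putting 0.05 straight into the spending function gives 0.0191, which does not match. So 0.0148 is two-sided, with 0.0074 in each tail.

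**2. Effect on error rates.** Over both looks the total error is 0.0500 counting both tails, and 0.0250 counting only claims of benefit. Ignoring the harm tail therefore does not inflate the chance of a false claim for Sentinel.

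**3. What a harm-side crossing needs.** The statistic is z = (difference in rates)/√[2p̄(1 − p̄)/1050], where p̄ is the pooled rate.
- 67 Sentinel vs 42 Control strokes: difference 25/1050 = 0.0238, p̄ = 109/2100 = 0.0519, standard error 0.00968, z = 2.46, P = 0.0139. It crosses.
- 66 vs 42: P = 0.0177. It does not cross.
- With fewer Control strokes, the smallest crossing counts are 55 vs 32 (P = 0.0118) and 40 vs 21 (P = 0.0136).

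**4. How often a mirrored boundary would act, and what it would save.** Stopping at 2100 spares at most 3000 − 2100 = 900 subjects, 450 of them on Sentinel. If review takes an assumed 2 to 3 months while enrollment continues, 200 to 300 more subjects enter. That leaves 600 to 700 spared, or 300 to 350 on Sentinel. Expected strokes avoided = Sentinel subjects spared × excess risk × chance of crossing.

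| True Sentinel rate (assumed), Control 4% | Chance of crossing (exact binomial) | Expected strokes avoided |
|---|---|---|
| 4% (no difference) | 0.74% | 0 |
| 4.5% | 3.0% | below 0.1 |
| 5% | 9.0% | about 0.3 |
| 6% | 36.9% | 2.2 to 2.6 |
| 7% | 72.5% | 6.5 to 7.6 |

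For the 6% row: 300 × 0.02 × 0.369 = 2.2 and 350 × 0.02 × 0.369 = 2.6.

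**5. Cost of a mirrored boundary.** At the design rates the chance of crossing on the harm side is about 1.4 × 10⁻⁷. Simulated power at 1500 per arm, without re-estimation, is 0.898 with or without it. A false stop for harm would occur 0.71% to 0.74% of the time for common rates of 2% to 4%. The boundary would be cheap but weak.

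**6. Could the sample size be raised after such a result?** From z = −2.44 at the interim, conditional power for benefit under the observed trend is effectively zero at N = 3000 and at N = 6000. Section 11.3.2 makes any increase depend on the interim results, and the methods paper cited for it (Bibliography, reference 37) concerns increases when interim results are promising. A significant reversal is the opposite case.

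**7. The provisions side by side.** Section 11.3.2 gives the effectiveness rule and the default. Section 21.3 puts the unblinded data before an independent monitor whose remit, by title, includes safety. Section 22.1 gives the power to stop at any stage to protect subjects, and the list in Section 22.1.1 is open. Together they allow a response to harm. They do not give it a number.

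**The case for a change.** The strongest reply is that permission is not a rule. Sections 22.1 and 22.1.1 leave the decision to the sponsor, and Section 21.3 cites the charter only for the sample size adaptation, so a harm rule in the charter cannot be assumed. Writing one would reuse an existing look and cost no efficacy alpha and almost no power. After a result at the harm boundary, conditional power for benefit at N = 3000 is about 10⁻⁸ even if all later subjects follow the design rates, so little is gained by going on. At N = 6000 it is about 27% on that same assumption, so an increase is not excluded on arithmetic alone.

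Part of this stands. The text gives no harm threshold and no reporting line, and the charter is unseen. But it does not show that the plan would go wrong. The 27% requires the full design benefit in every later subject just after a significant result the other way; few monitors would enlarge a trial on that basis. Nor is it clear that harm should need the same strength of evidence as benefit: a mirrored boundary would require nothing at 66 vs 42 strokes. Many statisticians would rather leave an adverse trend to an independent monitor's judgement than fix so strict a bound. A written rule would still end in a recommendation that the sponsor weighs under Section 22.1.

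**Conclusion.** No change is needed. The observation is correct: every interim stopping rule in the document is for benefit, and the literal default after a significant adverse result is to continue to the final analysis. But the two-sided level is computed correctly, the one-direction claim is coherent with it, and type I error for benefit (0.025) and power are unaffected.

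The missing harm action is a detail that the monitor and sponsor can be expected to supply, using powers already in Sections 21.3, 22.1 and 22.1.1. Using the effectiveness boundary for harm is at best a debatable trade-off: crossed 9.0% of the time at 5% vs 4%, 36.9% at 6% vs 4%, and 72.5% only at 7% vs 4%.

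This rests on three assumptions: that the monitor reports a significant excess of strokes to the sponsor, that the sponsor acts on it, and that the harmful Sentinel rates used here span the plausible range. If the charter already covers an adverse interim result, all that is missing from the protocol is a cross-reference.

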### 11.3.3. Subgroup Analyses

The primary endpoint and pre-specified additional measurements (see Section 6.2) will be summarized for the following subgroups.

- Operative risk (low, intermediate, high/extreme; treatment by subgroup interaction analysis)
- Gender

No adjustments for multiple comparisons will be made. Additional subgroup analyses may be performed as appropriate.

### 11.3.4. Justification of Pooling

Analyses for the primary endpoint will be presented using data pooled across centers and intended TAVR valve types. An assessment of the poolability of subjects across centers and intended TAVR valve types will be made using logistic regression. Main effects for the center (intended TAVR valve type) and treatment and the interaction of the center (intended TAVR valve type) by treatment will be included in separate logistic regression models with the primary endpoint as the outcome. If the *P* value for center (intended TAVR valve type) by treatment interaction is  $\geq 0.1$ , it can be concluded that the treatment effect is not different across the centers (intended TAVR valve types) and the data can be pooled. In the analysis to justify pooling across centers, the centers with fewer than 10 subjects enrolled in the study

will be combined into “virtual centers” based on geographic region so that “virtual centers” have  $\geq 10$  subjects but no more than the largest enrolling center.

### **11.3.5. Changes to Planned Analyses**

Any changes to the planned statistical analyses made prior to performing the analyses will be documented in an amended statistical analysis plan approved before performing the analyses. Changes from the planned statistical methods after performing the analyses will be documented in the clinical study report along with a reason for the change.

## **12. Health Economics Outcomes**

A formal health economics analysis may be completed as part of this study, provided meaningful healthcare resource utilization data are obtained. This will take into consideration healthcare resource utilization through discharge (with a maximum of 30 days if the subject is hospitalized for longer than 30 days) for both the Test and Control groups. Medical billing information (e.g., UB-04 billing claim form) through the TAVR index hospitalization may be collected at centers in the United States for health economics analyses.

## **13. Data Management**

### **13.1. Data Collection, Processing, and Review**

Subject data will be recorded in a limited access secure electronic data capture (EDC) system. Only personnel trained and authorized will have access to the system.

The clinical database will reside on a production server hosted by Medidata EDC System (New York, NY, USA). All changes made to the clinical data will be captured in an electronic audit trail and available for review by BSC or its representative. The associated RAVE software and database have been designed to meet regulatory compliance for deployment as part of a validated system compliant with laws and regulations applicable to the conduct of clinical studies pertaining to the use of electronic records and signatures. Database backups are performed regularly.

The Investigator provides his/her electronic signature on the appropriate eCRFs in compliance with local regulations. A written signature on printouts of the eCRFs must also be provided if required by local regulation. Changes to data previously submitted to BSC require a new electronic signature by the Investigator acknowledging and approving the changes.

Visual and/or electronic data review will be performed to identify possible data discrepancies. Manual and/or automatic queries will be created in the Medidata EDC system and will be issued to the center for appropriate response. Center staff will be responsible for resolving all queries in the database.

